7.7 EXTENT OF EXPOSURE

Descriptive statistics are planned for this section of the report based on the TS. The date and time of drug administration will be listed for each subject.

7.8 SAFETY ANALYSIS

All safety analyses will be performed on the TS.

If not stated otherwise, the safety results will be sorted by treatment group (combined SRD parts) or by actual treatment (FE part).

In the combined SRD parts, the placebo group under fasting (labelled “Placebo fast”) and the placebo group under fed conditions (labelled “Placebo fed”) will be analysed separately and compared, as well as the combined placebo group (labelled “Placebo total”) to all active treatment groups.

The safety data for treated subjects who failed to complete the study (dropouts or withdrawals) will be reported as far as their data are available. All withdrawals will be documented and the reason for withdrawal recorded.

7.8.1 Adverse events

AEs will be coded with the most recent version of MedDRA.

The analyses of AEs will be descriptive in nature and will be based on BI standards as presented in the corporate guideline: “Analysis and Presentation of Adverse Event Data from Clinical Trials” [001-MCG-156] (9).

The standard AE analyses will be based on the number of subjects with AEs (and not on the number of AEs).

For analysis multiple AE occurrence data on the CRF will be collapsed into an AE provided that all of the following applies:

- All AE attributes are identical (lower level term (LLT), intensity, action taken, therapy required, seriousness, reason for seriousness, relationship, outcome, AE of special interest)
- The occurrences were time-overlapping or time-adjacent (time-adjacency of 2 occurrences is given if the second occurrence started within one hour after end of the first occurrence)

For further details on summarization of AE data, please refer to [001-MCG-156] (9).

Section 5.2.2.1 of the CTP: *The following are considered as AESI in this trial:*

- *Hepatic injury, as defined by the following alterations of hepatic laboratory parameters:*
 - *An elevation of AST and/or ALT ≥ 3 -fold ULN combined with an elevation of total bilirubin ≥ 2 -fold ULN measured in the same blood sample, and/or*
 - *Marked peak aminotransferase (ALT, and/or AST) elevations ≥ 10 fold ULN*

The analysis of adverse events will be based on the concept of treatment emergent adverse events.

Section 5.2.2.2 of the CTP: *The REP for BI 705564, when measurable drug levels or PD effects are still likely to be present after the last administration, is not known for this first-in-human trial. Therefore, all AEs reported until the end of trial examination (last per protocol contact) will be considered on treatment [...].*

According to ICH E3 (10), AEs classified as ‘other significant’ needs to be reported and will include those non-serious and non-significant adverse events with (i) ‘action taken = discontinuation’ or ‘action taken = reduced’, or (ii) marked haematological and other lab abnormalities or lead to significant concomitant therapy as identified by the Clinical Monitor/Investigator at a Medical Quality Review Meeting.

An overall summary of AEs (including AESIs) will be presented.

The frequency of subjects with AEs will be summarized by treatment, primary system organ class (SOC) and preferred term (PT). Separate tables will be provided for subjects with other significant AEs according to ICH E3 (10), for subjects with serious AEs, for subjects with

drug-related AEs, for subjects with drug related serious adverse events and for subjects with AESIs.

The SOC and PTs will be sorted by frequency (within system organ class). The MedDRA version number will be displayed as a footnote in the respective output.

In addition, frequencies of subjects with non-serious AEs that had an incidence of > 5% for at least one treatment will be summarised by treatment, primary SOC and PT.

For disclosure of adverse events on EudraCT additional information not included in a standard AE analysis will be performed. The following three entries will be created:

- Adverse Events per arm for disclosure on EudraCT
- Non-serious Adverse Events for disclosure on EudraCT
- Serious Adverse Events for disclosure on EudraCT

7.8.2 Laboratory data

The analyses of laboratory data will be descriptive in nature and will be based on BI standards [001-MCG-157] ([11](#)).

Laboratory data will be analysed qualitatively via comparison of laboratory data to their reference ranges. Values outside the reference range as well as values defined as clinically relevant will be highlighted in the data listings.

Possibly clinically significant abnormal laboratory values are only those identified either in the Investigator's comments on the CRF or at the RPM/DBLM at the latest. It is the investigator's responsibility to decide whether a lab value is clinically significant abnormal or not. Standard or project-specific rules for flagging clinically significant values will not be applied in this study.

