**(3) Single rising dose part under *fed* conditions**

Visit	Day	Planned time (relative to drug administration) [h:min]	Approximate clock time of actual day [h:min]	Event and comment	Safety laboratory	PK  blood	PK  urine			12-lead ECG	Continuous ECG monitoring	Vital signs (BP, PR)	Questioning for AEs and concomitant therapy 
1	-21 to -1			Screening (SCR) 	x					x		x	
2	-3 to -1	-72:00 	08:00	Ambulatory visit	x								x
	1	-2:00	06:00	Admission to trial site  , allocation to treatment 	x 	x 	x 			x 	x 	x 	x 
		-0:30	07:30	High fat, high calorie breakfast									
		0:00	08:00	Drug administration			▲				▲		
		0:30	08:30			x				x 		x	x
		1:00	09:00			x				x 		x	x
		1:30	09:30			x				x 		x	
		2:00	10:00	240 mL fluid intake		x				x 		x	x
		3:00	11:00			x				x 		x	x
		4:00	12:00	240 mL fluid intake, thereafter lunch 	x	x	+			x 	▼	x	x
		6:00	14:00			x				x 		x	x
		8:00	16:00	Snack (voluntary) 		x	+			x 		x	x
		10:00	18:00			x							
		11:00	19:00	Dinner									
		12:00	20:00			x	+			x 		x	x
	2	24:00	08:00	Discharge from trial site, breakfast  (voluntary)	x	x	▼			x 		x	x
		34:00	18:00	Ambulatory visit		x						x	x
	3	48:00	08:00	Ambulatory visit	x	x				x 		x	x
	4	72:00	08:00	Ambulatory visit		x				x 		x	x
	6	120:00	08:00	Ambulatory visit									x 
	8	168:00	08:00	Ambulatory visit	x								x
	10	216:00	08:00	Ambulatory visit									x
4	11 to 15			End of trial (EOT) examination 	x					x		x	x

1. Subject must be informed and written informed consent obtained prior to starting any screening procedures. Screening procedures include physical examination, check of vital signs, ECG (including rhythm strip of at least 15 minutes), safety laboratory (including drug screening), demographics (including determination of body height and weight, smoking status and alcohol history), relevant medical history, concomitant therapy and review of inclusion/exclusion criteria. Pharmacogenetic samples will be collected, if needed.

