### 5.2.3 Assessment of safety laboratory parameters

For the assessment of laboratory parameters, blood and urine samples will be collected by the trial site at the time points indicated in the [Flow Charts](#) after the subjects have fasted for at least 10 h. Overnight fasting is not required at the discretion of the investigator or designee for retests or drug screening. In the single rising dose part under fed conditions, fasting is not applicable to the post-dose safety laboratory on Day 1.

The parameters that will be determined are listed in Tables 5.2.3: 1 and [5.2.3: 2](#). Reference ranges will be provided in the ISF, Section 10.

Manual differential white blood cell count or urine sediment examinations will only be performed, if there is an abnormality in the automatic blood cell count or in the urinalysis, respectively.

Table 5.2.3: 1 Routine laboratory tests

Functional lab group	Test name	SCR	A 	B 	C 	EOT
Haematology	Haematocrit	x	x	x	x	x
	Haemoglobin	x	x	x	x	x
	Red blood cell count (RBC)	x	x	x	x	x
	Reticulocyte count	x	--	--	x	x
	White blood cell count (WBC)	x	x	x	x	x
	Platelet count	x	x	x	x	x
Automatic WBC differential (relative and absolute)	Neutrophils, eosinophils, basophils, monocytes, lymphocytes	x	x	x	x	x
Manual differential WBC (if automatic differential WBC is abnormal)	Polymorphnuclear neutrophils (segs), band neutrophils (stabs), eosinophils, basophils, monocytes, lymphocytes					
Lymphocyte differentiation (relative and absolute; except for ratio)	T cells (CD3+), T helper cells (CD3+CD4+), cytotoxic T cells (CD3+CD8+), B cells (CD19+), natural killer cells (CD16+CD56+CD3-), double-positive T cells (CD3+CD4+CD8+), CD4:CD8 ratio	x	--	--	x 	x
Serum immunoglobulins	IgA	x	--	--	x	x
	IgG	x	--	--	x	x
	IgM	x	--	--	x	x
Coagulation	Activated partial thromboplastin time (aPTT)	x	x	x	x	x
	Prothrombin time (Quick's test and INR)	x	x	x	x	x
	Fibrinogen	x	--	x	x	x

 A: Days -3 to -1

 B: post-dose on Day 1 (single rising dose parts)

 C: Days 2, 3, 8 (single rising dose parts) and Day 2 (food effect part)

 Not on Day 3 (single rising dose parts)

Table 5.2.3: 1 Routine laboratory tests (cont'd)

Functional lab group	Test name	SCR	A 	B 	C 	EOT
Enzymes	Aspartate transaminase (AST/GOT)	x	x	x	x	x
	Alanine transaminase (ALT/GPT)	x	x	x	x	x
	Alkaline phosphatase (AP)	x	--	x	x	x

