### **7.3.4 Safety analyses**

Safety will be assessed for the endpoints listed in [Section 5.2.1](#). All treated subjects (i.e., all subjects who received at least one dose of study drug), will be included in the safety analysis. Safety analyses will be descriptive in nature and will be based on BI standards. No hypothesis testing is planned.

The analyses will be done by 'treatment at onset'.

Treatments will be compared in a descriptive way.

In the single rising dose parts, the placebo control group in the safety evaluation will consist of all placebo treated subjects, regardless of the dose group in which they were treated and regardless of whether they participated in the single rising dose part under fed or under fasting conditions; the active treatment groups will be compared to the placebo group in a descriptive way. To explore potential differences between placebo subjects under fasting and under fed conditions, these two subgroups will be compared descriptively.

In all (single rising dose – fasting and fed - and food effect) parts, tabulations of frequencies/proportions will be used for the evaluation of categorical (qualitative) data, and tabulations of descriptive statistics will be used to analyse continuous (quantitative) data.

Measurements (such as ECG, vital signs, or laboratory parameters) or AEs will be assigned to treatments (see [Section 4.1](#)) based on the actual treatment at the planned time of the measurement or on the recorded time of AE onset (concept of treatment emergent AEs).

Therefore, measurements planned or AEs recorded prior to first intake of trial medication will be assigned to 'screening', those between first trial medication intake until the end of trial visit will be assigned to the treatment period. These assignments including the corresponding time intervals will be defined in detail in the TSAP. Please note that AEs occurring after the last per protocol contact but entered before database lock will be reported to drug safety only and will not be captured in the trial database.

Additionally, further treatment intervals (analysing treatments) may be defined in order to provide summary statistics for time intervals, such as combined treatments, on-treatment totals or periods without treatment effects (such as screening and post-study intervals).

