Adverse events will be coded using the Medical Dictionary for Regulatory Activities (MedDRA). Frequency, severity and causal relationship of AEs will be tabulated by treatment, system organ class and preferred term. SAEs, AESIs (see [Section 5.2.2.1](#)) and other significant AEs (according to ICH E3) will be listed separately.

Laboratory data will be compared to their reference ranges. Values outside the reference range as well as values defined as clinically relevant will be highlighted in the listings. Additionally, differences from baseline will be evaluated.

Vital signs or other safety-relevant data observed at screening, baseline, during the course of the trial and at the end-of-trial evaluation will be assessed with regard to possible changes compared to findings before start of treatment.

For the single rising dose parts (under fasting and fed conditions) of the study, a centralised evaluation of all 12-lead ECGs recordings (see [Section 5.2.4](#)) will be the basis for the derivation of further ECG parameters based on the ECG variables QT, HR, QTcF, QTcB, PR, QRS, and RR. The baseline value of an ECG variable is defined as the mean of the triple ECG measurements prior to drug administration. The derivation of the quantitative and qualitative ECG endpoints and their analyses will be described in the TSAP.

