4. CHANGES IN THE PLANNED ANALYSIS OF THE STUDY

All analyses as planned in the CTP will be performed and are described in more detail in this TSAP.

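### Does SAP 7.8.2 lose the laboratory changes from baseline, and does pooled placebo distort the non-fasted Day 1 laboratory sample?

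*SAP*

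**What the plan says.** **Laboratory analysis.** After planning a comparison with reference ranges, Protocol 7.3.4 adds: "Additionally, differences from baseline will be evaluated". SAP 7.8.2 states: "Laboratory data will be analysed qualitatively via comparison of laboratory data to their reference ranges". It then covers highlighting in listings and the investigator's judgement of clinical significance, and refers to a corporate standard for the rest. It does not mention change from baseline, whereas SAP 7.8.3 (vital signs) and 7.8.4 (ECG) do. SAP 4 declares no departure from the protocol: "All analyses as planned in the CTP will be performed and are described in more detail in this TSAP". SAP 6.7 defines the laboratory baseline as the last value before the first dose.

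**Sampling condition.** Protocol 5.2.3 has laboratory samples taken "after the subjects have fasted for at least 10 h", with one exception: "In the single rising dose part under fed conditions, fasting is not applicable to the post-dose safety laboratory on Day 1". Flow Chart 3 places the meal ("High fat, high calorie breakfast") at -0:30 and the Day 1 laboratory sample at 4:00. In Flow Chart 1 the 4:00 sample precedes lunch, because meals come last at any time point, so it is fasted.

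**Comparator.** Protocol 7.3.4 forms the placebo group from all placebo subjects, "regardless of whether they participated in the single rising dose part under fed or under fasting conditions", and compares the active groups with it descriptively. It also compares fasted with fed placebo. SAP 7.8 repeats both: Placebo fast and Placebo fed "will be analysed separately and compared, as well as the combined placebo group" against all active groups. Table 6.1: 1 lists all three as treatment labels, and SAP 6.1 has laboratory tables shown by treatment with Placebo total included.

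**The concern.** There are two separate worries.

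First, the SAP says it describes the protocol's analyses in more detail, yet for laboratory change from baseline 7.8.2 gives none. A reader could infer that the analysis was dropped without being declared. Safety and tolerability are the primary objective of the single rising dose parts, and laboratory tests are a further criterion of interest.

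Second, at the Day 1 post-dose sample the fed active groups have eaten, but most of Placebo total has not. A change from a fasted baseline in those groups, or a count of out-of-range values, then contains a meal effect that the pooled comparator shares only in part. A reader could take the remainder for an effect of BI 705564. The fasting groups would show an offset in the other direction. Plasma glucose, lipase and amylase are among the tests taken at that sample.

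**Working it through.** **1. Is the change-from-baseline analysis lost?** Protocol 7.3.4 plans it. SAP 4 says every protocol analysis will be done. SAP 6.7 defines a baseline specifically for laboratory parameters, which a reference-range comparison alone would not need. SAP 7.8.2 defers to a corporate standard that is not available here. Read together, these indicate that the analysis is kept and not restated. Nothing shows that it was removed.

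**2. Group sizes.** From Protocol 3.1 and Tables 3.1: 1 and 3.1: 2, there are 6 fasting and 4 fed dose groups of 8, each with 2 on placebo, plus 12 food-effect subjects.
- Planned total: 6 × 8 + 12 + 4 × 8 = 92, as stated.
- Placebo: 6 × 2 = 12 fasted and 4 × 2 = 8 fed, 20 in all. The fed share is 8/20 = 0.4.
- With the two optional fed groups: 12 fasted and 12 fed, a fed share of 0.5.

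**3. Offset.** Let d be the meal effect on the 4 h change of a given test.
- Fed active minus Placebo total = drug effect + d - 0.4d = drug effect + 0.6d.
- Fasting active minus Placebo total = drug effect - 0.4d.
- With two extra fed groups: +0.5d and -0.5d.

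At 20, 40 and 80 mg, given in both parts, the fed-minus-fasting gap is 0.6d - (-0.4d) = d. Pooling does not create this gap. The same Placebo total is subtracted on both sides and cancels; the gap of d is already in the raw values. Placebo fed minus Placebo fast, which the SAP plans, estimates that same d without drug.

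**4. Reach.** Column B of Table 5.2.3: 1 lists 5 haematology, 5 differential, 3 coagulation, 8 enzyme, 7 substrate and 3 electrolyte tests, 31 in all. In 24 fed active subjects that is 31 × 24 = 744 values. This counts values collected; the documents do not show that every test responds to a meal. Triglycerides and total cholesterol are not taken at this sample. Of the five post-dose laboratory occasions (Days 1, 2, 3, 8 and end of trial), only Day 1 is exempt from the fasting rule.

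**5. Pooled or matched placebo for one fed group of 6.** In units of the SD of the change, assuming equal variances:
- Standard error against Placebo total: √(1/6 + 1/20) = √0.2167 = 0.465.
- Standard error against Placebo fed: √(1/6 + 1/8) = √0.2917 = 0.540, and 0.540/0.465 = 1.16.
- Mean squared error: (0.6d)² + 0.2167 for pooled, 0.2917 for matched.

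| Assumed d (SD) | Offset 0.6d | Offset / SE | MSE pooled | MSE matched |
|---|---|---|---|---|
| 0.25 | 0.15 | 0.32 | 0.239 | 0.292 |
| 0.50 | 0.30 | 0.64 | 0.307 | 0.292 |
| 1.00 | 0.60 | 1.29 | 0.577 | 0.292 |

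The two are equal when 0.36d² = 0.2917 - 0.2167 = 0.075, so d = 0.456. For a fasting group, 0.16d² = (1/6 + 1/12) - 0.2167 = 0.0333 gives the same value. The assumed range of 0.25 to 1.0 SD lies on both sides of it.

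**The case for a change.** The strongest case for a change is that it would be cheap. A sentence in 7.8.2 would make the laboratory section match those for vital signs and ECG, and naming the matched placebo group for one sample would use labels that already exist. The plan itself treats meal condition as relevant: it compares the two placebo subgroups and fits the ECG exposure-response model separately for fasting and fed doses. For a test with a strong meal response the pooled comparison is clearly the poorer one; at d = 1 SD its mean squared error is about twice that of the matched one (0.577 against 0.292).

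The facts in this stand: the SAP text is incomplete on its face, and Placebo total is a mixed comparator at this sample. The consequence drawn from them does not. No active-minus-placebo laboratory estimate, standard error or interval is planned, so the offsets describe a subtraction that a reader might make, not a result the trial will report. A reader who makes it has Placebo fed in the same set of treatment groups. Clinical significance is decided by the investigator without automatic flagging rules (SAP 7.8.2). The investigator knows the treatment (Protocol 4.1.5.2), and the protocol states that this sample is not fasted. Prescribing matched placebo for all 31 tests would also be the worse choice, by the same criterion, wherever d is small.

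**Conclusion.** No change to the plan follows. The missing change-from-baseline text is a gap in detail: the protocol, SAP 4 and the baseline definition in SAP 6.7 tell the analyst what to produce. A clarifying sentence there, or a table footnote that the fed-part Day 1 sample is not fasted, would do no harm but would alter no computed result.

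The mixed comparator is real but confined to one of five post-dose laboratory occasions in a descriptive display. Its offset is 0.6d for fed groups and -0.4d for fasting groups, or 0.5d each way if both optional fed groups are added. Placebo fast and Placebo fed are already shown and compared, so both the meal effect and the matched comparison can be read from planned output. Pooled against matched placebo is a fair trade-off between offset and precision, with the balance at about 0.46 SD. The primary endpoint is the number of subjects with drug-related adverse events, and no stopping criterion in Protocol 3.3.4.2 uses the comparison with Placebo total.

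This rests on the planned group sizes, equal variances across groups, and an assumed d, since the documents give none. It also takes SAP 4 at its word, because the corporate laboratory standard could not be consulted.

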### **3.2 DISCUSSION OF TRIAL DESIGN, INCLUDING THE CHOICE OF CONTROL GROUP(S)**

#### **Single rising dose parts under fasting and fed conditions**

For single-rising dose trials, the design described in [Section 3.1](#) is viewed favourable under the provision not to expose the subjects involved to undue risks since the main study objective is to investigate safety and tolerability of BI 705564.

With the rising dose design, single-blind conditions regarding the subject's treatment (active or placebo) are maintained within each dose group. However, the current dose level will be known to subjects and investigators. The disadvantage of this trial design is a possible observer bias with regard to the dose-depending effects as well as time effects but it has the virtue of minimizing subject risk by sequentially studying ascending doses. As time-effects are expected to be small relative to the differences between the doses in the broad range investigated, unbiased comparisons between treatments can still be expected.

It is standard in trials involving healthy volunteers to include a placebo group as control for the evaluation of safety, tolerability, and pharmacodynamics effects. Each dose group consists of 8 subjects with 6 on active treatment, and 2 on placebo. The placebo control group

includes all subjects of all dose groups treated with placebo. 6 subjects per active treatment group are in general considered as sufficient for the exploratory evaluation of pharmacokinetics.

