#### 4.1.5 Blinding and procedures for unblinding

##### 4.1.5.1 Blinding

The database of this trial will be handled open-label, because no bias with regard to data cleaning or safety measures is expected. This is considered acceptable because the potential for bias seems to be low and does not outweigh practical considerations.

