##### **Single rising dose parts under fasting and fed conditions**

The treatments administered (active or placebo) will be single-blind (blinded to subjects only). However, the current dose level will be known to the subjects.

The bioanalyst or analytical laboratory and the trial pharmacokineticist may receive the randomisation codes of the single rising dose part prior to official unblinding to perform the preliminary PK analysis. He or she will treat the codes confidentially.

In addition, the drug metabolism scientist may receive the randomisation codes prior to official unblinding to perform metabolites in safety testing analysis (MIST). He or she will confirm in writing that the codes will be treated confidentially.

Within the ECG laboratory, the staff involved with interval measurements and assessments will be blinded with respect to the treatment within each dose level and also with regard to the recording date and time as well as the time points of the ECGs. The interval measurements for a given subject will be performed in a random and blinded sequence by a single technician. No more than two different blinded readers will evaluate the ECGs of the study.

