#### **4.1.5.2 Procedures for emergency unblinding**

As this trial will be conducted single blinded (single rising dose parts under fasting and fed conditions) and open-label (food effect part), the treatment information will be known to the investigator. Therefore, no emergency envelopes will be provided.

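### SAP 7.8.2 leaves the clinically significant laboratory category to unblinded judgement and excludes rule-based flagging, so apart from hepatic injury no count of marked deviations by fixed thresholds is specified

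*SAP*

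**What the plan says.** SAP 7.8.2 defines the category narrowly. It states that "Possibly clinically significant abnormal laboratory values are only those identified either in the" investigator's CRF comments or at the combined report planning and database lock meeting. It makes it the investigator's "responsibility to decide whether a lab value is clinically significant abnormal or not", and closes with "Standard or project-specific rules for flagging clinically significant values will not be applied in this study".

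On who knows the treatment, protocol 4.1.5.2 covers all parts: "the treatment information will be known to the investigator". Protocol 4.1.5.1 adds: "The database of this trial will be handled open-label, because no bias with regard to data cleaning or safety measures is expected". For the single rising dose parts, protocol 3.2 concedes: "The disadvantage of this trial design is a possible observer bias with regard to the dose-depending effects as well as time effects".

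On what is displayed, protocol 7.3.4 says: "Values outside the reference range as well as values defined as clinically relevant will be highlighted in the listings". SAP 7.8.2 repeats this, and also compares all laboratory data with their reference ranges.

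**The concern.** Laboratory values are measured objectively, so a label that separates marked from trivial deviations can be defined without knowing the treatment. Here the label is given by people who know the treatment or can see it. The same value could be called significant on active and not on placebo, or the reverse.

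This matters most for the four measurements that protocol 2.3.2.7 lists among its precautions: lipase, amylase, platelets and CD19+ B cells. The judgement also reaches the primary endpoint of the single rising dose parts. A laboratory change becomes an adverse event only if the investigator finds it clinically relevant (protocol 5.2.2.2), and the endpoint counts subjects with drug-related adverse events. An objective count by treatment would give the reader something to set against those calls.

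**Working it through.** The plan gives no figure on this point, so the check sets the sections side by side.

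**1. Laboratory outputs that need no judgement**
- Reference-range comparison and highlighting of out-of-range values (SAP 7.8.2, protocol 7.3.4).
- Differences from baseline (protocol 7.3.4). SAP 7.8.2 does not restate them, but SAP 4 says that all protocol analyses will be done.
- Laboratory tables by treatment, including Placebo total (SAP 6.1), with N, mean, SD, minimum, median and maximum (SAP 7).
- Listings of every individual value, sorted by treatment group (SAP 7).
- The hepatic-injury event of special interest: AST or ALT at least 3 times ULN with bilirubin at least 2 times ULN in the same sample, or AST or ALT at least 10 times ULN (protocol 5.2.2.1). It has its own table (SAP 7.8.1).

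**2. Laboratory outputs that rest on judgement**
- The clinically significant flag (SAP 7.8.2).
- Laboratory-derived adverse events (protocol 5.2.2.2).
- Marked laboratory abnormalities among the other significant adverse events. The clinical monitor or investigator identifies these at a meeting, and no threshold is given (SAP 7.8.1).

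**3. Who judges.** That the investigator knows the treatment is explicit. For the database lock meeting it is an inference from the open-label database.

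**4. What the first list cannot supply.** A range flag treats a value just past the limit like one several times beyond it. The minimum and maximum show the extreme but not how many subjects reached a given level. A mean dilutes one affected subject among the six on active drug in a dose group. The listings hold all the information, but the reader would have to choose a cut-off after the fact and count by hand.

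**5. Comparison with ECG.** Central ECG readers are blinded to treatment within each dose level (protocol 4.1.5.1). QTc and QT are classified at fixed cut-offs of 450 and 500 msec (SAP 6.6). Categorical ECG endpoints get frequency tables (SAP 7.8.4). Outside hepatic injury, laboratory data have no counterpart.

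**6. Feasibility of thresholds.** Protocol 3.3.3 already uses numeric screening limits for B cells (40/µL) and platelets (100 cells/nL). This shows that such parameters can carry a number. It does not show which number suits a post-dose analysis.

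**7. Size.** Suppose a proportion p of subjects in both arms truly has a marked value, flagged with probability a on active and b on placebo. The false difference is p × (a − b). None of these inputs is in the documents. For assumed p of 0.10 to 0.30, a = 0.9 and b = 0.5 give 0.10 × 0.4 = 4 points to 0.30 × 0.4 = 12 points. Reversing a and b gives −4 to −12, and a = b gives 0. The sign and size follow entirely from the assumptions, so this shows the mechanism only.

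**The case against.** The strongest reply is that the laboratory safety assessment as a whole is sound. A reader might infer from SAP 7.8.2 that the entire laboratory signal depends on unblinded judgement, or that no planned output would reveal inconsistent calls. The documents do not support either reading. By-treatment tables with minimum and maximum would show a marked lipase rise or platelet fall whatever the investigator called it. The listings would show identical values labelled differently.

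Three further points stand:
- SAP 7.8.2 has clinically significant values highlighted in listings, and the documents specify no rate for them. A reader might note that one subject is 1/6 (16.7%) of a dose group on active drug, or 1/20 (5%) of pooled placebo. That is granularity in a rate the SAP does not plan to tabulate, and it does not measure bias.
- The excluded sponsor rules are not in the documents. The laboratory standard is only cited, so it cannot be presumed to cover pancreatic enzymes or CD19+ cells.
- A threshold table would not change adverse event reporting, which would still follow the investigator's judgement.

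The protocol also discloses possible observer bias and gives its reasons for open handling, and the safety analysis is descriptive with no hypothesis test. This lowers the stakes. It does not supply the missing count, and disclosing a bias is no reason to rule out an inexpensive objective check on it.

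**Conclusion.** The point holds in a limited form. The clinically significant laboratory category and the laboratory-derived adverse events rest on judgement made with knowledge of treatment. Rule-based flagging is expressly excluded. Outside hepatic injury, no count of subjects by fixed laboratory thresholds is specified. The rest of the laboratory analysis is unaffected.

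The conclusion rests on the text of SAP 7.8.2 read with the blinding sections, and on one inference: that the database lock meeting can see treatment. Neither the size nor the direction of any bias can be derived from the documents, and no bias is shown to have occurred. This is a worthwhile, low-cost improvement and not a flaw that invalidates the safety assessment.

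**What to change.** Replace the last sentence of SAP 7.8.2 with a supplementary analysis, for example:

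*In addition to the investigator's assessment, analysis-only thresholds for lipase, amylase, platelets and CD19+ B cells will be fixed before database lock. They will be taken from the sponsor's laboratory standard where it provides them, and otherwise stated as multiples of the reference limits or as changes from baseline. They will be applied to all post-dose values. The number of subjects meeting each threshold will be tabulated by treatment, including Placebo total, beside the number identified by the investigator.*

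The text should also state the baseline used for B cells. Protocol Table 5.2.3: 1 has no lymphocyte differentiation on Days -3 to -1, so under SAP 6.7 the baseline would normally be the screening value.

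Investigator judgement, adverse event reporting and clinical management stay as they are. The cost is a short SAP change and one extra table. Some flagged values in healthy men will be clinically trivial and will need a comment. Because the database is open, the thresholds should be dated and filed before anyone uses the post-dose laboratory data to choose them. If that is no longer possible, the table should be labelled post hoc.
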